13.0 Study Timelines*

13.1 *Describe the anticipated duration needed to enroll all study subjects.*

As previously described, we anticipate enrolling all 20 subjects within three months.

13.2 *Describe the duration of an individual subject's participation in the study. Include the length of study visits and overall study follow-up time.*

The duration of an individual subject's participation in the entire study (consent to the completion of focused-group interview) will be three months or less. There will be no physical study visits, only virtual study visits for Zoom participation and individual interview sessions.

- Enrollment, consenting, baseline data = 30 minutes
- Completion of all 8 sessions (60 min/each) = 480 minutes for the 8 weeks
- 20min/day practice for 8 weeks = 56 days X 20 min = 1,120 min = 18.7 hours over 8 weeks = 2.3 hours per week.
- Focused interview = 1 hour
- Questionnaires completion = 10 min X 8 weeks = 80 min total

13.3 *Describe the estimated duration for the investigators to complete this study (i.e. all data is collected and all analyses have been completed).*

The estimated duration for the investigators to complete this study will be about 12 months (recruitment, enrollment, intervention, data collection, data analysis).

14.0 Setting

14.1 *Describe all facilities/sites where you will be conducting research procedures. Include a description of the security and privacy of the facilities (e.g. locked facility, limited access, privacy barriers). Facility, department, and type of room are relevant. Do not abbreviate facility names.*

NOTE: Examples of acceptable response may be: "A classroom setting in the Department of Psychology equipped with a computer with relevant survey administration software," "The angiogram suite at Buffalo General Medical Center, a fully accredited tertiary care institution within New York State with badge access," or, "Community Center meeting hall."

All research procedures will be conducted from participants' private space (home) because we will deliver MMPH intervention via Zoom connection, video-recording viewing, and Mindfulness App use. Study participants will download the mindfulness App to their mobile devices. Research staff and interventionists will interact with study participants through Video conference connections from the privacy of their own work space.

14.2 *For research conducted outside of UB and its affiliates, describe:*

- *Site-specific regulations or customs affecting the research*
- *Local scientific and ethical review structure*

NOTE: This question is referring to UB affiliated research taking place outside UB, i.e. research conducted in the community, school-based research, international research, etc. It is not referring to multi-site research. UB affiliated institutions include Kaleida Health, ECMC, and Roswell Park Cancer Institute.

Response: NOT APPLICABLE

N/A: This study is not conducted outside of UB or its affiliates.

15.0 Community-Based Participatory Research

15.1 *Describe involvement of the community in the design and conduct of the research.*

NOTE: Community-Based Participatory Research (CBPR) is a collaborative approach to research that equitably involves all partners in the research process and recognizes the unique strengths that each brings. CBPR begins with a research topic of importance to the community, has the aim of combining

knowledge with action and achieving social change to improve health outcomes and eliminate health disparities.

Response: NOT APPLICABLE

N/A: This study does not utilize CBPR.

15.2 *Describe the composition and involvement of a community advisory board.*

Response: NOT APPLICABLE

N/A: This study does not have a community advisory board.

MMPH Interventionist who is familiar with the delivery of Mindfulness practice via Zoom to URM participants will be an integral member of the research team. They will assist the PI in content development and creating the AV recording of MMPH presentations and modules. In our current collaborative research projects (PI = [name]), we have identified four potential interventionists with these experiences that we can tap into based on their interests and availability.

CSE 611 Independent Project Course. In collaboration with the UB School of Engineering Professor, study PI will secure student interest in the MMPH App study. A dedicated group of engineering students will design and develop an MMPH mindfulness App for course credit during their enrollment in the Fall 2021 semester. We have full support from the UB SOE.

Describe other resources available to conduct the research.

16.2 *Describe the time and effort that the Principal Investigator and research staff will devote to conducting and completing the research.*

NOTE: Examples include the percentage of Full Time Equivalents (FTE), hours per week. The question will elicit whether there are appropriate resources to conduct the research.

Response: [name] (PI) will dedicate her full-time commitment to this project as she is a tenure-track Assistant [name] currently has a five credit-hours teaching commitment.

Co-I will dedicate 10% of her FTE to this project.

Per the contract, the UBSON will provide 10 hours per week of RA/ Clinical Research Coordinator time in this project.

MMPH Interventionists will dedicate 0.5 FTE for 26 weeks (6 months), including the time to design and review MMPH content, record the audio App and deliver the Zoom interventions. Their engagement in this project will also include training time to get familiar with the research protocol and time for re-trained if the study takes longer than anticipated.

16.3 *Describe the availability of medical or psychological resources that subjects might need as a result of anticipated consequences of the human research, if applicable.*

NOTE: One example includes: on-call availability of a counselor or psychologist for a study that screens subjects for depression.

Participants will be referred to their primary healthcare providers for further assessment if/when the need arises concerning participants' mental health needs. We will also provide community-based resources if they need additional support.

16.4 Describe your process to ensure that all persons assisting with the research are adequately informed about the protocol, the research procedures, and their duties and functions.

We will have at least monthly Research Team meetings to review participant recruitment, enrollment, research procedures, research-related issues. Team members will receive weekly updates about the overall progress of the study.

17.0 Other Approvals

17.1 Describe any approvals that will be obtained prior to commencing the research (e.g., school, external site, funding agency, laboratory, radiation safety, or biosafety).

Response:

N/A: This study does not require any other approvals.

18.0 Provisions to Protect the Privacy Interests of Subjects

18.1 Describe how you will protect subjects' privacy interests during the course of this research.

NOTE: Privacy refers to an individual's right to control access to him or herself. Privacy applies to the person. Confidentiality refers to how data collected about individuals for the research will be protected by the researcher from release. Confidentiality applies to the data.

Examples of appropriate responses include: "participant only meets with a study coordinator in a classroom setting where no one can overhear", or "the participant is reminded that they are free to refuse to answer any questions that they do not feel comfortable answering."

To protect participants' privacy interests and safety during the study, a research team member will only contact the participants on the phone in a private office where no one can overhear the conversation. Any email communications with participants will be kept private and confidential. All data collected during the study will be stored on a secure, password-protected cloud that only the research team has access to.

About Zoom communication, participants will meet with a study coordinator from the privacy of their home where no one can overhear the discussion about their participation in the study. Participants will be reminded not to discuss any personal information outside of the group discussion during the Zoom intervention.

The participant will be reminded that they are free to refuse to answer any questions that they do not feel comfortable answering.

18.2 Indicate how the research team is permitted to access any sources of information about the subjects.

*NOTE: Examples of appropriate responses include: school permission for review of records, consent of the subject, HIPAA waiver. This question **does apply** to records reviews.*

Sources of information about the subjects before enrollment will only be accessible to PH doctors. Once enrolled, research data will be stored in Research Files at UBSON, and only research team members (PI, co-I, RA) will have access. There will be no need for medical record review because the outcome data will be participant-reported outcomes (symptom presence, symptom severity, quality of life).

19.0 Data Management and Analysis*

19.1 Describe the data analysis plan, including any statistical procedures. This section applies to both quantitative and qualitative analysis.

As a pilot study, power analysis is not necessary. Statistical analysis will include descriptive statistics, mixed-effect modeling for repeated measures, and within-group and between-groups comparisons using t-tests or Wilcoxon signed-rank test as appropriate and Cohen's d effect size calculation. Multi-time data collection will be done via daily mobile-APP use.

We will follow the standard procedure in quantitative data analysis that includes general data inspection to verify the accuracy, completeness, and normality of the dataset using the SPSS23 program. We will compare clinical outcomes within-group (pre-post) as well as between groups in the post-intervention period. We will follow the recommendation of inappropriate statistical analysis and interpretation specific to each survey. For continuous variables, we will use a paired student t-test, independent t-test analytical approaches. For categorical variables and non-normally distributed variables, we will use non-parametric statistical methods (X2). Frequency distributions will be produced for all variables, and demographic information will be used to describe the sample. The impact of the M-App use on outcome variables will be analyzed using paired t-test and repeated measure ANOVA.

Qualitative data (focused-group interview data) will be analyzed using the standard qualitative thematic analysis procedure. We will transcribe the audio-recorded data and upload it into NViVo data management system. We will adhere to the thematic analysis method, described as follows:

1. A researcher will read and re-read the entire text to get a general sense of the participants' whole experience of being a student during the COVID-19 pandemic. While reading through the transcript, the researcher will take initial notes and perform a general review to get familiar with the data before analyzing the data.
2. The researcher will descriptively open code by dividing the significant text segments into 'meaningful units', keeping the participants' own words. The researcher will re-read all the codes again to eliminate redundancies.

The comparative discussion of these codes with other research team members to achieve a consensus will provide a validation step.

3. The researcher will use an inductive approach to look over the consensus codes, identify patterns among them, and start coming up with categories that describe 'critical moments,' significant aspects of the experiences.

4. The researcher will categorize the codes into overarching elements and higher-level categories and then cluster similar categories into the related themes. To make sure that the themes are useful and accurately represent the data, the researcher will return to the original data set and reflectively compare the categories against it.

5. The researcher will discuss with the research team members to refine the themes and develop the central theme. The researcher will then define and name the central theme by formulating its meanings and figuring out how it helps understand participants' experiences.

6. Finally, the researcher will develop an overall description of the essence of the participants' experience by merging the themes into the central theme/s in a flowing narration.

19.2 *If applicable, provide a power analysis.*

NOTE: This may not apply to certain types of studies, including chart/records reviews, survey studies, or observational studies. This question is asked to elicit whether the investigator has an adequate sample size to achieve the study objectives and justify a conclusion.

NOT APPLICABLE

19.3 *Describe any procedures that will be used for quality control of collected data.*

We will set up the required data entry field within the M-App and REDCap function to ensure that the data entry is accurate and complete. Erroneous (out-of-range) data entry will be less likely, as controlled by the proper setup of the data fields. Also, the system will remind participants to enter data into the required data field before proceeding to the following sections. A dedicated research coordinator will review data entry once a week to verify survey completion and confirm no missing data. In the case of missing data discovery, the research coordinator will contact and ask participants to complete it as soon as possible.

Before the data analysis process, two researchers will review the dataset for accuracy and discuss any possible reliability issues in data collection.

20.0 **Confidentiality***

A. Confidentiality of Study Data

Describe the local procedures for maintenance of confidentiality of study data and any records that will be reviewed for data collection.

20.1 A. Where and how will all data and records be stored? Include information about: password protection, encryption, physical controls, authorization of access, and separation of identifiers and data, as applicable. Include physical (e.g. paper) **and** electronic files.

With the use of M-App and REDCap programs, there will be minimal paper documentation of study data. In the rare instances where paper data collection is needed, they will be kept in a locked cabinet located in the PI's office ([name]). The paper documentation will contain only participant study numbers without an identifiable name. Record linking study ID numbers with their names will be kept in a separate locked cabinet.

We will upload data from M-App and REDCap into the SPSS and NVivo without any identifiable information. We will use only study ID numbers during data analysis.

We will upload audio voice recordings captured from Zoom directly to the NiVIVO database, locked and secured with password-protected access.

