2.0 Objectives*

2.1 *Describe the purpose, specific aims, or objectives of this research.*

Aim 1: To determine the feasibility and acceptability of the MMPH in community-dwelling URM adults with PH as a symptom self-management tool.

Aim 1a: Feasibility will be assessed by 1) frequency of home practice (> 2/week) and 2) retention rate (>70% of participants remaining at study completion).

Aim 1b: Acceptability will be determined by 1) participants' evaluation of the MMPH program (composite mean System Usability Scale score > 5, scale 1-7), 2) session completion rate (at least 6 of 8 [75% attendance] by the participants retained at the study end), and 3) qualitative thematic analysis of participants.

Aim 2: To determine the clinical impacts of an MMPH program in PH-symptom, anxiety, and depression reduction among community-dwelling URM adults with PH for symptom management.

2.2 *State the hypotheses to be tested, if applicable.*

NOTE: A hypothesis is a specific, testable prediction about what you expect to happen in your study that corresponds with your above listed objectives.

Hypothesis 1: MMPH will meet feasibility and acceptability targets for URM adults with PH

Hypothesis 2: Participants will report reductions in symptom severity of pain, anxiety, dyspnea, and fatigue at the end of the MMPH modules (short-term impacts). Participants will report decreases in the prevalence and intensity of PH-related symptoms, depression, and improved quality of life at the end of the MMPH program (long-term impacts).

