3.0 Scientific Endpoints*

3.1 *Describe the scientific endpoint(s), the main result or occurrence under study.*

*NOTE: Scientific endpoints are outcomes defined before the study begins to determine whether the objectives of the study have been met and to draw conclusions from the data. Include primary and secondary endpoints. Some example endpoints are: reduction of symptoms, improvement in quality of life, or survival. Your response should **not** be a date.*

Response: Symptom Severity Reduction per PAHSS and HRQOL improvement per EmPHasis-10.

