5.0 Study Design*

5.1 *Describe and explain the study design (e.g. case-control, cross-sectional, ethnographic, experimental, interventional, longitudinal, observational).*

This study will engage community-dwelling URM adults with PH living in the United States. We will use a two-group comparative study design where waitlisted participants will serve as controls. Considering a 20% attrition rate in a behavioral health intervention study, we aim to enroll a total of 20, with at least 16 participants to address study aims (8-10 in each Group).³⁴ As a pilot study, power analysis is not necessary. Statistical analysis will include descriptive statistics, mixed-effect modeling for repeated measures, and within-group and between-groups comparisons using t-tests or Wilcoxon signed-rank test as appropriate and Cohen's d effect size calculation. Multi-time data collection will be done via daily mobile-APP use.

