7.0 Local Number of Subjects

7.1 *Indicate the total number of subjects that will be enrolled or records that will be reviewed locally.*

Response: 20 participants

7.2 *If applicable, indicate how many subjects you expect to screen to reach your target sample (i.e. your screen failure rate).*

Response: Potentially eligible patients from UBMD clinic, URMC, RRH, as well as patients across the US from sources such as Research Match and Facebook will be screened by research team at UB. Potentially eligible and interested PH patients will self-refer and contact us for screening. We will also invited PH patients across the US to participate in the study using additional recruitment sources such as Research Match, across the US CTSA Hub advertisement, and

Social media (Facebook) advertisement. With the approved amendment to include all ethnicity, we will be able to reach the target enrollment goal as planned. Our enrollment goal is 20 patients.

7.3 *Justify the feasibility of recruiting the proposed number of eligible subjects within the anticipated recruitment period. For example, how many potential subjects do you have access to? What percentage of those potential subjects do you need to recruit?*

Response: An enrollment rate to a mind-body intervention is approximately 30%, yielding about 103 participants. Considering a 15% attrition rate, we will enroll 20 participants to achieve at least 8 in each Group. We received verbal agreements from PH specialists at these locations to assist in referring, of eligible participants in the study.

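### Sections 5.1 and 19.1 name no suitable non-parametric test for comparing non-normal PAHSS and EmPHasis-10 scores between the MMPH and waitlist groups

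*Combined protocol and SAP*

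**What the plan says.** Section 3.1 sets two endpoints: "Symptom Severity Reduction per PAHSS and HRQOL improvement per EmPHasis-10". Section 5.1 describes a two-group comparison with waitlisted participants as controls.

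Sections 5.1 and 19.1 share one sentence on tests, which plans "within-group and between-groups comparisons using t-tests or Wilcoxon signed-rank test as appropriate", with Cohen's d as the effect size. Mixed-effect modelling for repeated measures is listed in the same sentence.

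Section 19.1 then defines the comparisons: "We will compare clinical outcomes within-group (pre-post) as well as between groups in the post-intervention period". It names a paired and an independent t-test for continuous variables. For the rest it says "For categorical variables and non-normally distributed variables, we will use non-parametric statistical methods (X2"), and chi-square is the only method given in that sentence.

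No Mann-Whitney, Wilcoxon rank-sum or other independent-samples rank test appears anywhere in the document.

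**The concern.** The signed-rank test works on differences within pairs. That suits change within a person, but not a comparison of two groups of different people. The document describes no matching, and the independent t-test in section 19.1 treats the groups as independent.

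Chi-square suits categorical outcomes, such as the symptom prevalence in hypothesis 2 (section 2.2: "Participants will report decreases in the prevalence and intensity of PH-related symptoms"). Applied to a score, it treats each value as an unordered category, and the plan defines no cut-points.

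The non-normal branch is a real part of the plan. Section 19.1 inspects the data for normality and sends variables that fail to a different method. An analyst who reached that branch for PAHSS or EmPHasis-10 would have to pair strangers, run chi-square on an ordered score, or leave the written plan. At stake is the post-intervention between-group comparison of both stated endpoints.

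**Working it through.** **The plan's own figure.** Section 5.1: "Considering a 20% attrition rate in a behavioral health intervention study, we aim to enroll a total of 20", with at least 16 retained. 16 / (1 − 0.20) = 20, which reproduces. Section 7.3 uses another rate: "Considering a 15% attrition rate, we will enroll 20 participants to achieve at least 8 in each Group". 16 / (1 − 0.15) = 18.8, so 19, which is consistent with enrolling 20. No alpha, effect size or allocation ratio is stated.

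**The two readings of the shared sentence.**

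| Reading | Between-group method named for a non-normal score | Problem |
|---|---|---|
| Signed-rank covers both kinds of comparison | Signed-rank (and chi-square in the later sentence) | Paired test, no pairs |
| "As appropriate" limits signed-rank to pre-post change | Chi-square only | Ignores order |

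Both readings end without a suitable test.

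**Can signed-rank be run between groups?** It needs equal group sizes. Assume 10 v 10 enrolled and independent dropout at rate a. Then P(unequal) = 1 − Σ over k of [Bin(k; 10, 1 − a)]².

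- a = 0.15: 1 − 0.254 = 0.746.
- a = 0.20: 1 − 0.224 = 0.776.
- Given that both groups keep at least 8: 0.650 and 0.620.
- If exactly 4 of 20 are lost at random: 1 − C(10,2)²/C(20,4) = 1 − 2025/4845 = 0.582.

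With unequal groups, participants would have to be discarded. Section 22.3 says the study will try to use all available data.

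**If sizes happen to be equal.** The p-value depends on who is paired with whom. One simulated 8 v 8 dataset gave signed-rank p from 0.008 to 0.109 across re-pairings, against a single rank-sum p of 0.021.

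Simulated power at two-sided 0.05, with an assumed 1 SD shift and continuous scores without ties:

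| Case | Signed-rank on arbitrary pairs | Exact Mann-Whitney | Independent t-test |
|---|---|---|---|
| 8 v 8, normal | 35% | 44% | 46% |
| 8 v 8, exponential | 45% | 63% | 54% |
| 10 v 10, normal | 50% | 51% | 56% |
| 10 v 10, exponential | 58% | 71% | 62% |

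Type I error at 8 v 8 is about 4% for signed-rank, about 5% for Mann-Whitney, and 5.0% (normal) or 4.3% (exponential) for the t-test. None is inflated.

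**Chi-square taken literally.** With N distinct scores, Pearson's statistic equals N on N − 1 degrees of freedom, whatever their order. At N = 16 (8 v 8), p = 0.38 even if every score in one group exceeds every score in the other. Exact Mann-Whitney gives 2/C(16,8) = 2/12,870 = 0.00016 for the same data. This illustrates the loss of order. It assumes no ties and does not forecast a real result.

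**The case against.** The strongest defence is that the shared sentence is a compressed list. "As appropriate" may assign signed-rank to pre-post change, where it is correct. Section 19.1 names both a paired and an independent t-test, so the authors know the difference. This stands in part: the between-group rank test may be missing rather than misnamed. It does not rescue the rule, because chi-square is then all that remains.

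It can also be said that allocation is not described. If waitlisted participants later received MMPH, their own wait-versus-treated comparison would be paired. The document does not describe that crossover, and the planned comparison is between groups and comes with an independent t-test. The groups being unmatched remains an inference, though a well-supported one.

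Third, little depends on this test. Aim 1 is feasibility and acceptability, hypothesis 2 is worded as participants' own change, and the independent t-test, mixed model and Cohen's d are already planned. This stands, and it limits the severity.

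Fourth, the pairing and power figures assume that someone invents pairs, which a careful analyst would not do. Part of the 8 v 8 gap also comes from the tests' discrete levels. With Mann-Whitney held to about 3.8%, its power is 39% rather than 44% for normal data (against 35%), and 58% rather than 63% for exponential data (against 45%). Both points stand.

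A reader might infer that the plan has no valid between-group analysis, or that its results would carry inflated false-positive rates. The documents and the figures support neither.

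**Conclusion.** The point holds as a wrong rule with modest consequences. For a non-normal PAHSS or EmPHasis-10 score, sections 5.1 and 19.1 lead to a paired test without pairs or to chi-square on an ordered score. The document does not show which of these the authors meant, and the conclusion does not depend on it.

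The clearest practical size is the 75% to 78% chance that signed-rank could not be run between groups without discarding people (62% to 65% if both groups keep at least 8). That rests on assumed 10 v 10 enrolment and independent dropout at the plan's own rates. The power losses are secondary: they need equal groups and invented pairs, and they almost vanish at 10 v 10 with normal data.

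The problem arises only if scores are judged non-normal, and valid parametric routes remain in a 20-person pilot that makes no power claim. It should be corrected, but it does not undermine the study.

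**What to change.** Make the same change in sections 5.1 and 19.1:

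1. Limit the Wilcoxon signed-rank test to within-person pre-post change.
2. Name the exact Mann-Whitney (Wilcoxon rank-sum) test for between-group comparison of non-normal PAHSS and EmPHasis-10 scores.
3. Limit chi-square to categorical variables such as symptom presence, and use Fisher's exact test at 8 to 10 per group.

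The cost is two or three sentences, with no new data and no change in sample size. If scores are in fact normal, Mann-Whitney has slightly less power than the t-test: 46% − 44% = 2 percentage points at 8 v 8 and 56% − 51% = 5 at 10 v 10, for the assumed 1 SD shift.

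### Cohen's d is planned at 8–10 per group with no small-sample correction, no confidence interval and no named standardiser

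*Combined protocol and SAP*

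**What the plan says.** Sections 5.1 and 19.1 contain the same line on effect sizes: "within-group and between-groups comparisons using t-tests or Wilcoxon signed-rank test as appropriate and Cohen's d effect size calculation". Section 19.1 then names the contrasts: "We will compare clinical outcomes within-group (pre-post) as well as between groups in the post-intervention period". It also names the tests: "For continuous variables, we will use a paired student t-test, independent t-test analytical approaches". So d is to be computed for a paired pre-post contrast and for an independent-groups contrast.

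The numbers are small by design. Section 5.1 plans enrolment "with at least 16 participants to address study aims (8-10 in each Group"), and section 7.3 also gives at least 8 per group. Section 19.1 adds "As a pilot study, power analysis is not necessary", and section 19.2 marks a power analysis as not applicable.

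No section says which SD standardises d (pooled, baseline, or SD of change), whether d is corrected for small samples, or whether an interval accompanies d or any outcome difference.

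**The concern.** The primary objective in section 1.0 includes preliminary impacts, and Aim 2 in section 2.1 concerns clinical impact on symptoms, anxiety and depression. With no powered test behind Aim 2, readers will lean on the effect estimates. Three separate gaps bear on how far they can do so:

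- **No interval.** At this size a single d says little about the true effect, and nothing in the plan would show that.
- **No small-sample correction.** Cohen's d is biased away from zero, and the bias grows as degrees of freedom fall.
- **No standardiser.** A paired d is often divided by the SD of change, and a between-group d by an SD between people. If both conventions were used, the same mean change in points would give two different values of d.

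What is at stake is whether the Aim 2 effect sizes can be interpreted. The feasibility and acceptability targets are not affected.

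**Working it through.** **Inputs.** 20 enrolled, at least 16 retained, 8–10 per group (sections 5.1 and 7.3). Contrasts and tests are from section 19.1. The documents give no target effect, outcome SD or pre-post correlation r. The d of 0.5 used below is illustrative, and r is assumed over a range.

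**1. The plan's own figure.** Section 5.1: 16 / (1 − 0.20) = 20, which reproduces the enrolment target. Section 7.3 uses 15% attrition: 16 / 0.85 = 18.8, or 19, and 20 × 0.85 = 17 retained. Both rates support 20 enrolled. The two rates should be reconciled, but this does not affect the point here.

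**2. Small-sample bias.** The Hedges factor is J(df) = Γ(df/2) / [√(df/2) · Γ((df − 1)/2)]. Uncorrected d has expectation (true value)/J. For two groups df = 2n − 2. For a paired d divided by the SD of change, df = n − 1.

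| Contrast | n | df | J | Average inflation, 1/J − 1 | Observed 0.50 becomes |
|---|---|---|---|---|---|
| Between groups | 8 per group | 14 | 0.945 | 5.8% | 0.47 |
| Between groups | 10 per group | 18 | 0.958 | 4.4% | 0.48 |
| Paired, SD of change | 8 | 7 | 0.888 | 12.6% | 0.44 |
| Paired, SD of change | 10 | 9 | 0.914 | 9.4% | 0.46 |

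**3. Bias against sampling error.** In 400,000 simulated trials with a true between-group d of 0.5, the mean d was 0.529 (8 per group) and 0.523 (10 per group). The excess is 0.029 and 0.023, against sampling SDs of 0.55 and 0.48, or about one-twentieth of an SD. A single d exceeded 0.5 in about 51% of trials, and in about 49% after correction. When the true effect is zero the bias is zero.

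**4. Precision.** The 95% interval inverts the noncentral t distribution. For an observed between-group d of 0.5, t = 0.5/√(2/n), which is 1.00 at n = 8 and 1.12 at n = 10.

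- Between groups: −0.51 to 1.49 (n = 8, width 2.00); −0.40 to 1.38 (n = 10, width 1.78).
- Paired, SD of change, observed 0.5: −0.25 to 1.22 (n = 8); −0.17 to 1.15 (n = 10).

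**5. Standardiser.** With equal pre and post SDs, SD of change = SD × √(2(1 − r)). A paired d on the SD of change is therefore 1/√(2(1 − r)) times the d on the raw-score SD.

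| Assumed r | 0.3 | 0.5 | 0.7 | 0.8 | 0.9 |
|---|---|---|---|---|---|
| Ratio | 0.85 | 1.00 | 1.29 | 1.58 | 2.24 |

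The two scales agree at r = 0.5. Below that the paired d is the smaller one, and above it the larger.

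**The case against.** The strongest reply is that this is a feasibility pilot and the plan is merely brief. Section 19.1 also provides descriptive statistics, mixed models, t-tests and repeated-measures ANOVA. Section 3.1 defines the endpoints by the symptom and quality-of-life scales, and section 2.1 sets separate numerical targets for feasibility and acceptability. The between-group bias is a few hundredths of a d unit and is swamped by sampling error. All of this stands, and it limits the weight of the point.

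Three stronger readings are tempting, and the documents do not support them:

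- A reader might infer that the plan exaggerates the programme's effect. The bias exists only on average, is small between groups, and vanishes if there is no effect. A missing interval hides imprecision but does not inflate d.
- A reader might infer that the within-group and between-group values cannot be compared because they use different denominators. The plan is silent on the denominator, and one raw-score SD for both would be consistent with its text. Nor is the paired d always larger: that needs r above 0.5, and no r is given.
- A reader might infer that a later trial would be sized on an inflated d. No section says that d will be used for sample size, or that the two values will be set against each other.

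The reply does not fill the gap. The text names d for both contrasts and leaves out the correction, the interval and the standardiser.

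**Conclusion.** The point holds as an under-specified analysis with a better method at almost no cost. Its parts, in order of importance:

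1. **Imprecision not shown.** The between-group interval around an observed 0.5 is 1.8 to 2.0 d units wide and takes in both harm and large benefit. This needs no assumption about r; it rests on 8–10 per group, normal outcomes and equal variances.
2. **Possible difference in scale.** This arises only if the paired d uses the SD of change. The ratio then runs from 0.85 to 2.24 over assumed r of 0.3 to 0.9.
3. **Small-sample bias.** About 4–6% between groups, and 9–13% for a paired d on the SD of change.

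A shared scale would not make the two contrasts equivalent: one is a change within a group, the other a difference between groups after the intervention. Severity is minor for a feasibility pilot.

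**What to change.** In sections 5.1 and 19.1:

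- Replace Cohen's d with Hedges' g and its 95% confidence interval.
- Report the raw-score mean difference with its 95% confidence interval beside each g.
- Name one raw-score standardiser for both contrasts, for example the pooled baseline SD of the two groups. Take the correction from the degrees of freedom of that SD: 14 with 16 participants, 18 with 20, so J is 0.945 to 0.958. The paired factors of 0.888 and 0.914 no longer apply.
- For the paired effect, use an interval that allows for the pre-post correlation. The noncentral-t interval used for two groups does not carry over directly.
- State that the pre-post change and the between-group difference estimate different things even on one scale.

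The cost is about one sentence in each section. No new data are needed, since Table 1 in section 12.1 already places the symptom, quality-of-life, depression and mindfulness questionnaires in the first week. This assumes that waitlisted participants complete the same forms, because the table is not split by group. The correction makes reported effects slightly smaller. If the SD of change would otherwise have been used, the common standardiser may move the paired value either way, depending on r.
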